6.2.17.3 Definition of ≥30% and ≥50% Responder

Subjects who achieve a percent reduction in NRS score relating to 'Average pain intensity related to DPN in the past 24 hours' of \geq 30% (programmatically, where the change from baseline value is \leq -30) at Week 12 will be classified as responders, and non-responders otherwise.

Similarly, subjects who achieve a percent reduction in NRS score relating to 'Average pain intensity related to DPN in the past 24 hours' of \geq 50% (programmatically, where the change from baseline value is \leq -50) at Week 12 will be classified as responders, and non-responders otherwise.

Subjects with missing weekly mean NRS score relating to 'Average pain intensity related to DPN in the past 24 hours' at Week 12 will be classified as non-responders.

6.2.17.4 Time to First ≥30% and ≥50% Reduction

The time to first \geq 30% (and \geq 50%) reduction in NRS score relating to 'Average pain intensity related to DPN in the past 24 hours' will be identified as follows.

A moving average of the NRS average pain intensity will be calculated, that is, average NRS score for moving 7-day intervals from Day 1 to Day 7, from Day 2 to Day 8, from Day 3 to Day 9, and so on, up to the final interval of Day 78 to Day 84.

Percentage reduction from Baseline Mean NRS (as defined in Section 6.2.17.1) for each moving average interval will be calculated using the percentage change from baseline method described in Section 6.2.15.

The first moving average interval that yields a reduction from baseline of $\geq 30\%$ (and $\geq 50\%$) will be identified and the last day of this block of 7 days will be the date of first $\geq 30\%$ (and $\geq 50\%$) reduction.

Subjects who failed to achieve the target reduction (\geq 30% and \geq 50%) will be censored on the day of the last non-missing average pain intensity score, or the Week 12 visit date (whichever is later), for that subject.

Subjects who discontinued the study prior to Week 12 and who failed to achieve the target reduction ($\geq 30\%$ and $\geq 50\%$) while on the study will be censored at the time of discontinuation.

Time to the first \geq 30% (and \geq 50%) reduction (days) will subsequently be obtained as follows:

Date of first \geq 30% (and \geq 50%) reduction – date of dosing of study drug

6.2.18Daily Sleep Interference Scale

The Daily Sleep Interference Scale (DSIS) is a single-item measure with 11-point response scale (0-10; where 0 corresponds to "did not interfere with sleep" and 10 corresponds to "completely interfered with sleep/unable to sleep due to pain) that quantify sleep interference due to pain. The subjects complete this questionnaire daily upon awakening each morning.

Baseline mean score will be obtained as described in Section 6.2.2. Weekly mean DSIS data will be obtained for Week 12 data (and prior weeks) based on the subjects actual Week 12 visit date.

If the subject's Week 12 visit date is within Day 80 to Day 88, then data on the actual Week 12 visit date up to 6 days prior to this date will be the corresponding data for Week 12 visit date. Consequently, the Week 11 data will be obtained by counting 7 days backwards from the 1st day of Week 12, Week 10 NRS scores will be obtained by counting 7 days backwards from the 1st day of Week 11, and the process continue up to Week 1. If the subject's actual Week 12 visit date is beyond Day 88, then the corresponding data from Day 82 to Day 88, inclusive, will be the Week 12 data. Similar process as described previously will be used to obtain the data for each week from Week 11 up to Week 1. Meanwhile, if the subject's actual Week 12 visit date is earlier than Day 80, then no Week 12 data will be identified.

Timing of Week 12 Visit	Reference Day (DSIS or Rescue Medication)
Day 80 to Day 88	Count backwards from day of Week 12 visit
Day 89+	Count backwards from Day 88 only
Earlier than Day 80	No Week 12 data identified

For subjects that withdraw early or have missing data such that they do not have any data that would fall into the Week 12 windowing, their last non-missing diary day will serve as the anchor, as described in Section 6.2.17.2.

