Kandomize eligible subjects		X				
Dispense study drug		Х		Х	Х	
First dose of study drug (in the clinic)		Х				
Confirm daily study drug dosing in past 24 hours each morning p		Х	Х	Х	Х	Х
Return study drug and assess compliance m				Х	Х	Х
Pain Catastrophizing Scale (PCS)		Х				X
Brief Pain Inventory for Diabetic Peripheral Neuropathy (BPI- DPN)		Х		Х		Х
Norfolk Quality of Life Questionnaire – Diabetic Neuropathy (QOL-DN)		Х		Х		X
Patient Global Impression of Severity (PGI-S)	Х	Х				
Patient Global Impression of Change (PGI-C)				Х	Х	Х
Sheehan-Suicidality Tracking Scale (S-STS)	Х	Х	$\mathbf{X}^{w}$	Х	Х	Х
Misuse, Abuse, and Diversion Drug Event Reporting System ® (MADDERS) r			Х	Х	Х	Х
Concomitant medications	Хq	Х	Х	Х	Х	Х
Adverse events S	Х	Х	Х	Х	Х	Х
Safety follow-up calls						X x

Clin	ical Protocol Amendment #7 Masked NYX-2925-2008 25 June 202
a)	Subjects will discontinue all concomitant analgesic medications taken for pain related to diabetic peripheral neuropathy. Duration of the period will depend upon the analgesic(s) being discontinued, not to exceed 4 weeks. Subjects not taking any concomitant analgesic medications at Visit 1 may directly begin Week -1 of the Screening Period.
(q	ET=Early Termination. Subjects who prematurely discontinue randomized treatment will have Week 12 procedures performed. Diary completion ends the night before the Week 12 visit.
c)	Informed consent includes an additional consent for inclusion in a secure, proprietary, research subject database to screen for protocol violators. The main informed consent document may be executed up to 30 days prior to the screening visit. The date the first screening related activity is completed will be considered the subject's screening date. If the subject does not complete the screening visit within 30 days of signing the informed consent document the subject must be reconsented.
(p	Verify subject still meets all inclusion criteria and does not meet any exclusion criteria.
e)	Review of these educational materials via the aLearn portal will be repeated for all subjects at each site-based visit, with the exception of the final visit. Training at Visit 3 is per Investigator discretion. An ongoing blinded data review (e.g., if pain score variability is increased on a subject or site level) will be conducted to monitor these metrics [Analgesic Solutions, Wayland, MA].

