4 SAMPLE SIZE

The planned sample size is a total of 204 randomized subjects. This will provide approximately 80% power to detect a difference in means of 0.73 assuming that the common standard deviation is 1.7 (and accounting for 15% drop-out rate), using two-sided statistical testing with an overall Type I error rate of 0.05.

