6.2.17.1 Baseline Mean NRS Score

The baseline mean NRS score is defined as the average of the NRS scores on the last 7 days prior to the first dose of study drug (Study days -7 to -1). A minimum of 5 non-missing NRS scores out of the 7 days is required for the baseline mean NRS score.

Baseline NRS = Sum of daily NRS scores (over 7 days)/ Number of available diaries

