9 CHANGES TO PLANNED PROTOCOL ANALYSIS

- 1. The primary endpoint was clarified from "change from baseline in the weekly mean NRS score assessing average pain intensity related to DPN in the past 24 hours" to "change from baseline to Week 12 in the weekly mean NRS score assessing average pain intensity related to DPN in the past 24 hours.".
- 2. For the primary efficacy analysis, intercurrent event handling, missing data will not be imputed (using baseline observation carried forward [BOCF], as described in the protocol), and the missing values will be assumed to follow the missing-at-random (MAR) mechanism.
- 3. The secondary efficacy endpoint "Change from baseline in the weekly mean of the daily Numerical Rating Scale (NRS) at each week from Week 1 through Week 12" was updated to "Change from baseline in the weekly mean Numerical Rating Scale (NRS) score assessing average pain intensity related to DPN at each week from Week 1 through Week 12".

- 4. One of the other efficacy endpoints was updated as follows "Change from baseline in the weekly mean NRS score assessing average pain intensity upon walking in the past 24 hours from baseline"
- 5. The other efficacy endpoint "Change from baseline in the mean NRS score for daily worst pain intensity related to DPN" was updated to "Change from baseline in the weekly mean NRS score assessing worst pain intensity related to DPN"
- 6. Other efficacy endpoint "Change from baseline to Week 12 in Norfolk Quality of Life Questionnaire Diabetic Neuropathy (QOL-DN) domain scores" was added.
- 7. The time to first ≥30% (and ≥50%) reduction will be identified based on a moving average of the NRS average pain intensity, that is, NRS average from Day 1 to Day 7, from Day 2 to Day 8, from Day 3 to Day 9, up to from Day 78 to Day 84. The first moving average that yields a reduction from baseline of ≥30% (and ≥50%) will be identified and the last day of this block of 7 days on which the reduction was identified will be the time to first of ≥30% (and ≥50%) reduction which is different to how the weekly NRS is define for the primary endpoint, and any other efficacy endpoints based on the daily NRS scores.
- 8. Censoring of the subjects who failed to achieve the target reduction (≥30% and ≥50%) was changed from "the time of their final week with NRS pain intensity measurements" to "the day that the last available NRS pain intensity score was recorded"

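### SAP 6.2.17.4 sets no minimum diary count for the moving 7-day windows in the time-to-response analysis, so a nearly empty window can count as a first response, and some non-responders stay at risk without data.

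*SAP*

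**What the plan says.** **Event.** SAP 6.2.17.4 takes the "average NRS score for moving 7-day intervals from Day 1 to Day 7, from Day 2 to Day 8" and so on, one day at a time, with Day 78-84 as the last interval. The first window that reaches the target is the event, dated to that window's last day. The section gives no minimum number of scores and does not say how a window with missing days is averaged. It does not tie the last window to the subject's last diary.

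**Contrast within the SAP.** For the baseline mean, 6.2.17.1 states: "A minimum of 5 non-missing NRS scores out of the 7 days is required for the baseline mean NRS score". The formula there divides by the number of diaries available.

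**Censoring.** In 6.2.17.4, subjects who do not reach the target are censored at "the day of the last non-missing average pain intensity score, or the Week 12 visit date (whichever is later". A separate sentence covers those who left before Week 12 without reaching the target during their participation; they are censored at discontinuation. Section 9 item 8 gives the adopted censoring date as "the day that the last available NRS pain intensity score was recorded" and does not mention the Week 12 visit. Those words are the new rule in item 8, not the superseded one, so the two statements compete within the current SAP.

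**Diary.** Footnote b of the protocol's Table 3 says: "Diary completion ends the night before the Week 12 visit".

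**The concern.** A 7-day mean is meant to damp day-to-day noise. Without a minimum count, that protection disappears where diaries are sparse: inside a gap, or in windows that trail the last entry. One low score can then be the whole average. The later-of censoring rule has the opposite fault, because it treats days without a diary as observed days without response.

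Both faults depend on missing diaries. If diary adherence or dropout differed between arms, the curves and the comparison would be distorted. The outputs affected are Tables 14.2.3.4 and 14.2.3.5 and Figures 14.2.1.5 and 14.2.1.6. In addition, two programmers could follow the text faithfully and produce different events.

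**Working it through.** **The plan's own figure.** The documents give no size or power for this endpoint. SAP Section 4 sizes the primary comparison: "approximately 80% power to detect a difference in means of 0.73", "assuming that the common standard deviation is 1.7", "using two-sided statistical testing with an overall Type I error rate of 0.05", with 15% dropout.
- Per arm: 2 × (1.960 + 0.842)² × 1.7² / 0.73² = 85.1, rounded up to 86.
- With dropout: 86 / 0.85 = 101.2, rounded up to 102 per arm, or 204 in total. This reproduces the plan.
- 15% of 204 is about 31 expected dropouts.

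**Worked case 1: windows after the last diary.** Assume baseline 6.0, every score 6 except a 4 on the last diary, Day 30, and averaging of available scores. The ≥30% target is a mean of at most 0.7 × 6 = 4.2.

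| Window | Scores | Mean | Change |
|---|---|---|---|
| Day 24-30 | 7 | 5.71 | -4.8% |
| Day 25-31 | 6 | 5.67 | -5.6% |
| Day 26-32 | 5 | 5.60 | -6.7% |
| Day 27-33 | 4 | 5.50 | -8.3% |
| Day 28-34 | 3 | 5.33 | -11.1% |
| Day 29-35 | 2 | 5.00 | -16.7% |
| Day 30-36 | 1 | 4.00 | -33.3% |

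The literal rule records a ≥30% response on Day 36, six days after the last score. With a final score of 3, the last row gives -50.0% and a ≥50% response. With at least 5 of 7 scores required, neither event occurs.

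**Worked case 2: diary gap.** Scores of 6 to Day 20, a lone 4 on Day 27, and 6 again from Day 34. Window Day 21-27 holds one score and gives -33.3%, so a response is dated Day 27. A 5-of-7 minimum removes it.

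**Worked case 3: completer seen before Day 84.** For a Day 80 visit the last diary is Day 79. Windows ending Days 80 to 84 hold 6, 5, 4, 3 and 2 scores. If the scores on Days 78 and 79 are 4 and all others 6, the full window Day 73-79 has mean (5 × 6 + 2 × 4)/7 = 5.43, or -9.5%. Window Day 78-84 has mean 4.0, or -33.3%, and the event is dated four days after the final visit.

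**Censoring arithmetic.** Diary stopped on Day 30, visit on Day 84: 84 - 30 = 54 days at risk without a score. Ordinary completer: last diary the night before the visit, so 1 day.

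**Chance of a false ≥30% response in one subject.** This is a simulation with 20,000 subjects per setting, true change zero, baseline 6, integer scores and day-to-day correlation 0.4. The SDs and the correlation are assumptions; the documents give none.

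| Last diary | Rule | SD 0.8 | SD 1.2 | SD 1.5 |
|---|---|---|---|---|
| Day 20 | 7 of 7 | 0% | 1.8% | 7.6% |
| Day 20 | at least 5 of 7 | 0.1% | 2.6% | 9.7% |
| Day 20 | any available score | 3.3% | 13.0% | 24.0% |
| Day 79 | 7 of 7 | 0.1% | 9.2% | 31.0% |
| Day 79 | any available score | 0.6% | 13.7% | 37.4% |
| Day 83 | at least 5 of 7 | 0.1% | 10.1% | 32.6% |
| Day 83 | any available score | 0.1% | 10.1% | 32.6% |

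For ≥50% with last diary Day 20, averaging any available score gives 0.1%, 1.8% and 5.2%.

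**Trial level.** The assumptions are baseline 6, mean change -1, between-subject SD 1.7, 15% dropout and diary compliance 80-95%, with 3,000 subjects per scenario. The literal rule was compared with a 5-of-7 minimum whose windows also stop at the last diary.
- ≥30%, daily SD 0.7-1.5: event rates 46.2-62.6% against 44.7-59.7%. The extra responders are 1.4-2.9% of subjects, or 2.9-5.8 per 204, and 7-12% of dropouts gain a response. Of all events, 2.3-3.4% are dated after the last diary.
- ≥50%, daily SD 0.7-1.0 only: extra responders 1.2-2.8% of subjects, or 2.4-5.7 per 204.

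The comparator is slightly stricter than the fix below, which keeps trailing windows with 5 or 6 scores. The literal rule was also run without the discontinuation sentence. Both choices make the extra counts, if anything, too high.

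**The case against.** **Early leavers may already be covered.** The sentence on early discontinuers can fairly be read to reject a crossing dated after exit, since it was not achieved during participation. A reader might infer from the window rule alone that the SAP certainly credits responses to people who have left; the documents do not support that. On this reading, part of the Day 20 result disappears. The sentence does not reach diary gaps, the interval between the last diary and a later recorded discontinuation, or completers seen before Day 84.

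**Averaging available scores is an inference.** The SAP does not say how a partly filled moving window is averaged. Requiring all 7 scores, or carrying over the 5-of-7 minimum along with the baseline divisor, would remove one-score responses. This stands, and it is why the text needs a rule.

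**Completers are little affected.** With a full diary, a Day 80 completer's trailing windows never hold fewer than 2 scores. At the nominal Day 84 visit the single trailing window holds 6, and a 5-of-7 minimum changes nothing. Much of the Day 79 false-response rate is ordinary noise: at SD 1.5, complete windows alone give 31.0% of the 37.4%. Censoring one day late is trivial, and censoring after Day 84 cannot alter a log-rank test because no event can be dated later. All of this stands.

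**The 54-day case has no known frequency.** Staff review diary compliance at the visits, so such subjects may be few.

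**Bias between arms is not shown.** A reader might infer a biased treatment comparison. That requires missingness that differs by arm, and the documents give no figures for it. The public SAP also lacks the analysis section for other efficacy endpoints; the log-rank test comes from the protocol synopsis, which allows another applicable test.

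**Conclusion.** The point holds as a gap in the derivation. If available scores are averaged, SAP 6.2.17.4 lets a window with one or a few scores define a first response, dated up to 6 days after the last score. Its censoring rule keeps diary-stoppers who attend Week 12 at risk without data and does not match Section 9 item 8.

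The effect is small: about 3-6 extra ≥30% responders per 204, concentrated in dropouts. That size rests on the assumed baseline, diary variability, compliance and dropout pattern. The endpoint is an other efficacy endpoint, and Section 9 item 10 makes no multiplicity adjustment for it. The primary MMRM and the sample size are unaffected. The correction is still worth making, because the text allows different programs to produce different events and the remedy is cheap.

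**What to change.** In SAP 6.2.17.4:

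1. Evaluate a moving interval only if it has at least 5 of 7 non-missing scores, the SAP's own baseline minimum. Date a response no later than the last non-missing score in that interval, and count none after discontinuation. Do not require windows to end by the last diary: that would drop Day 78-84 for a completer seen on Day 84, although the window holds 6 of 7 scores.
2. Censor every non-responder, early discontinuers included, at the last non-missing average pain score, no later than Day 84. This replaces both the Week 12 visit alternative and the discontinuation date, and agrees with Section 9 item 8.

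The cost is two sentences of SAP text and one programming condition, with slightly fewer events and slightly shorter follow-up.

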6.2.19 Rescue Medication

Use of rescue medication (number of tablets taken) is recorded daily at bedtime in the handheld diary. Weeks will be identified and assigned using the same method as described in Section 6.2.17.2 for NRS data. For each week, the total number of tablets reported per week will be summed and percentage of rescue-free days per week will be obtained.

A subject using rescue medication is defined as any subject who recorded one or more tablets in the daily diary at any time after the first dose of study drug.

Percentage of rescue-free days per week will be obtained by taking the number of days where rescue medication was answered 'No' in the daily diary and divided by the number of non-missing diary entries for the week.

Weekly dosage of acetaminophen (mg) will be calculated using the total number of tablets taken for each week multiplied by 500 mg.

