6.2.17.2 Post-Baseline Weekly Mean NRS Scores

Weekly Mean NRS Scores for Week 12 (and prior weeks) will be obtained based on the subject's actual Week 12 visit date. If the subject's Week 12 visit date is within Day 80 to Day 88, then the 7th NRS score for Week 12 will be the corresponding NRS score on the day before the subject's Week 12 visit date, and the 6th to 1st NRS score for Week 12 will be obtained backwards from this. Thus, the corresponding NRS scores on the last 7 days prior to Week 12 actual visit date will be used for Week 12. Consequently, the Week 11 NRS scores will be obtained by counting 7 days backwards from the 1st NRS score for Week 12, Week 10 NRS scores will be obtained by counting 7 days backwards from the 1st NRS score for Week 11 and continuing up to Week 1. If the subject's actual Week 12 visit date is beyond Day 88, then the corresponding NRS score on the day before Day 88 (i.e., Day 87) will be used as the 7th NRS score for Week 12, and the 6th to 1st NRS score will be obtained backwards from this and continuing for each week from Week 11 to Week 1. Meanwhile, if the subject's actual Week 12 visit date is earlier than Day 80, then no Week 12 data will be identified.

Timing of Week 12 Visit	Reference Day (NRS)
Day 80 to Day 88	Count backwards from day before Week 12 visit
Day 80 to Day 88	(Week 12 study day -1)

Day 89+	Count backwards from Day 87 only	
Earlier than Day 80	No Week 12 data identified	

For subjects that withdraw early or have missing data such that they do not have any data that would fall into the Week 12 windowing, their last non-missing diary day will serve as the anchor; weeks will be counted backwards in 7-day intervals from the last day. For the week ending with this anchor day, study week will be assigned such that the majority of days fall in the nominal week. For example, Week 11 is nominally day 71-77; if a subject's last value is on day 74, the majority of the resulting 7-day window working backwards would be in "Week 11", so their last week would be analyzed as "Week 11" and the subsequent intervals assigned descending weeks working backwards. The following table shows how the last interval will be assigned based on its last day.

Timing of Last Non-Missing Diary	Assigned Week
	(from which to count backwards)
Day 1 to Day 10	Week 1
Day 11 to Day 17	Week 2
Day 18 to Day 24	Week 3
Day 25 to Day 31	Week 4
Day 32 to Day 38	Week 5
Day 39 to Day 45	Week 6
Day 46 to Day 52	Week 7
Day 53 to Day 59	Week 8

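### Weekly rescue dose is an undivided sum, so missing diary days count as zero; the week windows conflict, Week 1 can reach before the first dose, and the model omits baseline rescue use

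*SAP*

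**What the plan says.** **Weekly amount.** SAP 6.2.19 states: "For each week, the total number of tablets reported per week will be summed". It then states: "Weekly dosage of acetaminophen (mg) will be calculated using the total number of tablets taken for each week multiplied by 500 mg". The section sets no minimum number of entries and no missing-day rule for these totals. Its percentage of rescue-free days, by contrast, is "divided by the number of non-missing diary entries for the week".

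**Week windows.** SAP 6.2.19 also says: "Weeks will be identified and assigned using the same method as described in Section 6.2.17.2 for NRS data". Under SAP 6.2.17.2, for a Week 12 visit on Days 80 to 88, "the 7th NRS score for Week 12 will be the corresponding NRS score on the day before the subject's Week 12 visit date". Earlier weeks follow by "counting 7 days backwards from the 1st NRS score for Week 11 and continuing up to Week 1". The table in SAP 6.2.18, however, has a column headed "Reference Day (DSIS or Rescue Medication", and it anchors on the visit day itself (Day 88 for later visits). Rescue is recorded at bedtime, and a footnote to Protocol Table 3 ends the diary on the night before the Week 12 visit.

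**Pre-dose days.** A rescue user is someone who "recorded one or more tablets in the daily diary at any time after the first dose of study drug". That post-dose limit is attached to the yes/no measure only, not to the weekly totals.

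**Analysis.** SAP 6.11.2.5 summarises weekly tablets (Table 14.2.2.5) and fits an MMRM to the weekly dose, with a treatment difference and p-value at each week (Table 14.2.2.8). The model has site, treatment, week and their treatment-by-week term, and no baseline. Under Protocol 6.1, rescue use is recorded daily from Week -1.

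**The concern.** The amount of rescue used is a named secondary endpoint, and readers will use it to interpret the pain result. A total over reported days mixes two things: how much rescue was taken and how often the diary was completed. If completion or week length differs between arms, the arm with more gaps appears to use less rescue. The SAP allows for missing days in rescue-free days and in the weekly NRS means, but not here.

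The two window rules allow two different Week 12 totals from the same data. With no rule for pre-dose days, Week 1 is either a short week or one containing baseline use; a total is sensitive to that choice. Leaving out baseline rescue costs precision but does not bias a randomized comparison.

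**Working it through.** **The plan's own figure.** The documents give no number for the rescue endpoint. The primary sample size reproduces: difference 0.73, SD 1.7, two-sided 0.05 and 80% power (SAP 4) give 86 per arm; 86/0.85 = 101.2, so 102 per arm and 204 in total. Evaluable per arm is 204 × 0.85/2 = 86.7, taken as 87 below.

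**1. Under-count per week.** With d of 7 entries and steady use, the total falls short by 1 − d/7:
- 6 entries: 14.3%
- 5 entries: 28.6%
- 4 entries: 42.9%
- 7 entries: 0%

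At the instructed limit of 4 tablets, one missing day hides at most 4 × 500 = 2,000 mg.

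**2. Effect on the arm comparison.** With mean use u tablets/day and completion c unrelated to use, the expected total is c × 7 × u × 500 mg.
- Equal completion multiplies a true difference by c: it shrinks by 5%, 10% or 20% at 95%, 90% or 80%.
- Unequal completion with equal use gives a false difference of (gap) × 7 × u × 500. A 5-point gap gives 87.5, 175 or 350 mg/week at an assumed 0.5, 1 or 2 tablets/day.

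**3. Illustrative simulation.** There were 4,000 runs with all inputs assumed: subject mean tablets/day gamma with mean 1 and CV 1, daily count binomial out of 4, subject completion beta with concentration 10, and 87 per arm.

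| Scenario | Plain total | Prorated |
|---|---|---|
| No effect, 95% vs 90% completion | 177 mg, 6.9% rejections | 6 mg, 5.0% |
| No effect, 95% vs 85% completion | 344 mg, 11.3% rejections | −2 mg, 5.6% |
| True difference 0.3 tablets/day, 90% in both arms | 907 mg, power 58.0% | 1,006 mg, power 59.5% |

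Repeat runs of the first two scenarios gave 6.4% to 6.6% and 9.9% to 12.2% rejections for the plain total.

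**4. Week 12 window.** For a visit on Day v from 80 to 88, the NRS anchor covers Days v−7 to v−1, which can hold 7 entries. The 6.2.18 table covers Days v−6 to v, but the last diary is on Day v−1, so it holds at most 6. At an assumed 1 tablet/day, a fully compliant subject goes from 3,500 to 3,000 mg, a loss of 1/7. For visits from Day 89 the table uses Days 82 to 88 and 7 entries are possible.

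**5. Week 1 window.** Week 1 lies 77 days before Week 12, and there is no Day 0.

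| Visit day | NRS anchor: Week 1 | Pre-dose days | Visit-day anchor: Week 1 | Pre-dose days |
|---|---|---|---|---|
| 80 | −5 to 2 | 5 | −4 to 3 | 4 |
| 81 | −4 to 3 | 4 | −3 to 4 | 3 |
| 82 | −3 to 4 | 3 | −2 to 5 | 2 |
| 83 | −2 to 5 | 2 | −1 to 6 | 1 |
| 84 | −1 to 6 | 1 | 1 to 7 | 0 |
| 85 | 1 to 7 | 0 | 2 to 8 | 0 |
| 88 | 4 to 10 | 0 | 5 to 11 | 0 |

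A visit exactly on schedule (Day 84) is already affected under the NRS anchor. Some early withdrawals are too: a last diary on Days 1 to 6 brings in 6 down to 1 pre-dose days, and on Days 11 to 13 it brings in 3, 2 and 1.

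**6. Baseline covariate.** The confidence interval narrows by 1 − √(1 − r²): 4.6%, 13.4% or 28.6% at assumed correlations of 0.3, 0.5 or 0.7.

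**The case against.** - **The harm is conditional.** Nothing in the documents suggests that completion will differ by arm. The trial is double-blind, adequate diary compliance is required for randomization, and compliance is reviewed throughout. With equal completion, power barely moves. This stands, and it limits the size of the problem. It does not supply the missing rule.
- **The title of Table 14.2.2.8 speaks of a weekly mean dose.** That may mean a group mean. A title cannot override an explicit derivation, so it adds an ambiguity and does not settle the matter.
- **The window conflict may be a stray label.** The dedicated rescue section adopts the NRS method, so the 6.2.18 heading is probably a slip. Even so, a programmer cannot follow both, and the correction is a deletion.
- **Pre-dose days are arguably excluded already.** Section 6.2.17.2 concerns post-baseline weeks, and SAP 6.2.2 assigns Days −7 to −1 to baseline. That is the natural reading, but it is not written. The gap also affects the NRS weeks. A total is more exposed than a mean, because dropping days shortens the week.
- **Omitting baseline is not an error.** Correct: it is a precision point only. The DSIS and QOL-DN models do adjust for baseline.
- **Proration is noisy in sparse weeks.** One entry of 4 tablets would become 4 × 7 × 500 = 14,000 mg. This is a real cost of the remedy.
- **The endpoint is minor.** It is one of several secondary endpoints, has no multiplicity control, and is described only descriptively in the protocol synopsis. This bears on priority and does not make the derivation right.

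**Conclusion.** The concern holds in all four parts. As written, the weekly tablets and dose are under-counted by about 1/7 per missing diary day in partly completed weeks. The conflicting windows permit two Week 12 totals, and the content of Week 1 is undefined for some subjects. The comparison between arms is biased only if completion or week length differs by arm; otherwise differences shrink in proportion to completion, with little loss of power. The milligram and rejection figures rest on assumed tablet use and completion, and on missing days resembling observed days. The window counts and the 1/7 fraction follow directly from the documents. Baseline adjustment is a matter of precision. The primary analysis and N = 204 are untouched. This should be corrected before the rescue tables are programmed.

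**What to change.** 1. **SAP 6.2.19.** Replace the totals with: *Weekly tablets = 7 × (tablets on non-missing diary days from Day 1 onward ÷ number of such days). Weekly dose (mg) = weekly tablets × 500. A week with no such entries is missing. The minimum number of entries is the one applied to post-baseline weekly NRS.* Section 6.2.17.2 currently sets no minimum, so at present one post-dose entry would suffice; any threshold added there would carry over. Apply this to Tables 14.2.2.8 and 14.2.2.5, or footnote the latter as an unscaled reported count.
2. **SAP 6.2.18 table.** Remove the mention of rescue medication from the column heading, so that only the NRS window governs rescue weeks.
3. **SAP 6.11.2.5.** Add baseline rescue dose (Days −7 to −1, prorated the same way from pre-dose entries) as a covariate in the rescue MMRM.

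The cost is SAP wording, one derivation used in two tables, and one model term. All the data are already collected. The downside is that proration assumes missing days resemble observed ones, and short weeks become noisier: Week 1 for a Day 80 visit would scale 2 days by 7/2 = 3.5.
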